9.1 PRIMARY ENDPOINT

The primary endpoint for this study is:

- Annualized rate of severe exacerbation events during the 52-week placebo-controlled treatment period.

9.2 SECONDARY ENDPOINTS

9.2.1 Key Secondary Efficacy Endpoint

- Change from Baseline in pre-bronchodilator % predicted FEV1 at Week 12.

9.2.2 Secondary Efficacy Endpoints

- Change from Baseline in pre-bronchodilator % predicted FEV1 at Weeks 2, 4, 8, 24, 36, and 52 and other time points assessed.
- Time to first severe exacerbation event during 52-week treatment period.
- Time to first LOAC Event during 52-week treatment period.

- Change from Baseline in other lung function measurements (absolute and relative FEV₁, AM/PM peak expiratory flow, FVC, forced expiratory flow (FEF) 25-75%, post-bronchodilator % predicted FEV₁) at Weeks 2, 4, 8, 12, 24, 36, 52, and other time points assessed.
- The effect of dupilumab on healthcare resource utilization (HCRU)
- Change from Baseline at Weeks 2, 4, 8, 12, 24, 36, and 52 and other timepoints in:
 - Morning/evening asthma symptom score (electronic diary)
 - PRO:
 - ACQ-IA, for children 6 to <12 years old,
 - Use of reliever medication
 - Number of nocturnal awakenings due to asthma symptoms requiring the use of reliever medication
- Change from Baseline at Weeks 12, 24, 36, 52, 64 in:
 - PRO:
 - Paediatric Asthma Quality of Life Questionnaire with Standardised Activities–Interviewer Administered (PAQLQ(S)-IA) score, for children ≥7 to <12 years old at Randomization Visit 2.

9.2.2.1 Disease-specific Efficacy Measures

9.2.2.1.1 Spirometry

A spirometer that meets the 2005 American Thoracic Society (ATS)/European Respiratory Society (ERS) recommendations will be used. Spirometry should be performed in accordance with the ATS/ ERS guidelines (8). For pre-bronchodilator measured parameters, including FEV₁, peak expiratory flow (PEF), FVC and FEF 25-75%, spirometry will be performed after a wash out period of bronchodilators according to their action duration, for example, withholding the last dose of salbutamol/albuterol or levosalbutamol/levalbuterol for at least 6 hours, withholding the last dose of LABA for at least 12 hours, and withholding the last dose of LAMA for at least 24 hours. This will be verified before performing the PEF measurements.

For post-bronchodilator FEV₁, the measure should follow the steps as that at screening test for reversibility validation.

At all visits, spirometry will be performed either in the AM or PM, but preferred in the AM, and the spirometry should be done at approximately the same time at each visit throughout the study. The same spirometer and standard spirometric techniques, including calibration, will be used to perform spirometry at all visits and, whenever possible, the same person should perform the measurements.

Pulmonary function tests will be measured in sitting position; however, if necessary to undertake the testing with the subject standing or in another position, this should be noted on the spirometry report. For any subject, the position should be consistent throughout the study.

Three measurements fulfilling the ATS acceptability and repeatability criteria should be obtained at every visit, if possible. The acceptability criteria must be applied before the repeatability criteria. Unacceptable maneuvers must be discarded before applying the repeatability criteria. If a subject fails to provide repeatable and/or acceptable maneuvers, an explanation should be recorded.

The largest FEV1 and largest FVC should be recorded after the data are examined from all of the acceptable curves, even if they do not come from the same curve. The FEF 25-75% should be obtained from the single curve that meets the acceptability criteria and gives the largest sum of FVC plus FEV1 (best test).

Automated best efforts, which combine FEV1 and FVC are not acceptable.

The spirometer must be calibrated following the principles of the ATS/ERS guidelines every day that a study subject is seen and spirometry is carried out. The calibration records should be kept in a reviewable log. It is preferred that the calibration equipment (ie, 3-liter syringe) that is used to calibrate the spirometer be subjected to a validated calibration according to the manufacturer's specifications.

Further details on spirometry will be available in a separate operational manual provided to the sites.

9.2.2.1.2 Reversibility/Post-bronchodilator FEV1

Reversibility is defined as an increase in absolute FEV1 of 10% over the baseline value, demonstrated within 30 minutes of bronchodilator administration.

At the screening test, reversibility is tested after the administration of 200 to 400 mcg (2 to 4 puffs) of albuterol/salbutamol or 45 to 90 mcg of (2 to 4 puffs) levalbuterol/levosalbutamol reliever medication from a primed MDI (up to 3 opportunities during the same visit are allowed with a maximum of 12 puffs of reliever medication, if tolerated by the patient). Documented reversibility or positive airway hyperresponsiveness to methacholine within 12 months prior to Visit 1 is considered acceptable.

All reversibility tests will be administered after pulmonary function testing and after asthma medications have been withheld for the appropriate intervals. Patients will receive the albuterol/salbutamol or levalbuterol/levosalbutamol reliever medication as puff inhalations using the respective MDI. Alternatively, and only if it is consistent with usual office practice (to be documented), reversibility testing may be performed using inhalation of nebulized albuterol/salbutamol or levalbuterol/levosalbutamol reliever medication.

The spirometry for measuring absolute FEV1 may be repeated several times within the 30 minutes after administration of bronchodilator.

Reversibility is an inclusion criterion, but if the subject does not meet this reversibility criterion at Screening Visit 1, up to 2 additional assessments can be performed at any time between Screening and Baseline Visit 2.

For post-bronchodilator FEV1 at remaining study visits following randomization, the measure should follow the steps as that at screening test for reversibility validation except a maximum of 4 puffs of reliever medication can be used. If other attempt for reversibility test was performed at Baseline Visit 2, then the post-bronchodilator FEV1 will come from the result of this reversibility test.

9.2.2.2 Disease-specific, Daily Efficacy Assessments

9.2.2.2.1 Electronic Diary/PEF meter

On a daily basis throughout the study, the patient uses an electronic diary/PEF meter to:

- Measure morning and evening PEF.
- Respond to the morning and evening asthma symptom scale questions.
- Indicate the number of inhalations/day of salbutamol/albuterol or levosalbutamol/levalbuterol for symptom relief.
- Record the number of inhalations/day of background product used.
- Record the number of nocturnal awakenings due to asthma symptoms requiring the use of reliever medication.
- Record oral steroids use for exacerbation event.

At Screening (Visit 1), patients and parent(s)/caregiver(s)/legal guardian(s) will be issued an electronic diary/PEF meter. Parent(s)/caregiver(s)/legal guardian(s) will be instructed on the use of the device, and written instructions on the use of the electronic PEF meter will be provided to the parent(s)/caregiver(s)/legal guardian(s). In addition, the Investigator will instruct the parent(s)/caregiver(s)/legal guardian(s) on how to record the following variables in the electronic PEF meter:

- AM PEF performed within 15 minutes after arising (between 5:30 AM and 11:59 AM) prior to taking any albuterol/salbutamol or levalbuterol/levosalbutamol reliever medication)
- PM PEF performed in the evening (between 5:30 PM and 11:59 PM) prior to taking any albuterol/salbutamol or levalbuterol/levosalbutamol reliever medication)
- Patient/Parent(s)/caregiver(s)/legal guardian(s) should try to withhold albuterol/salbutamol or levalbuterol/levosalbutamol reliever medication for at least 6 hours before performing the PEF measurements.
- Three PEF efforts will be performed by the patient; all 3 values will be recorded by the electronic PEF meter, and the highest value will be used for evaluation

Baseline AM PEF will be the mean AM measurement recorded for the 7 days prior to the first dose of investigational product, and baseline PM PEF will be the mean PM measurement recorded

for the 7 days prior to the first dose of investigational product. Period stability limit is defined as the respective mean AM or PM PEF obtained over the last 7 days prior to Day1. There should be at least 4 days' measurement for setting up the stability limit, and the first dosing visit should be rescheduled until data for 4 days are available.

Baseline reliever use will be the mean number of reliever use recorded for the 7 days prior to the first dose of investigational product. Period stability limit is defined as the respective mean AM or PM PFE obtained over the last 7 days prior to Day1. There should be at least 4 days' measurement for setting up the stability limit, and the first dosing visit should be rescheduled until data for 4 days are available for both measurements.

Information derived from the electronic PEF meter will be evaluated by the Investigator at study visits.

9.2.2.2.2 Asthma Symptom Numerical Rating Scale (NRS) Score

Parent(s)/caregiver(s)/legal guardian(s) will record overall symptom scores in an electronic diary/PEF meter twice a day prior to measuring PEF. The patient's overall asthma symptoms experienced during the waking hours will be recorded in the evening (PM symptom score). Baseline symptom scores will be the mean AM and mean PM scores recorded for the 7 days prior to randomization. The baseline AM/PM symptom score will be computed following the same algorithm used for baseline AM/PM PEF. Scores range between 0-4 with 0 indicating more mild symptoms and 4 indicating more severe symptoms. There is no global score, just an AM score and a PM score. A Minimal clinically important difference (MCID) of 0.35 is being used (9) (see [Appendix E](#)).

9.2.2.2.3 Use of Reliever Medicine

The number of salbutamol/albuterol or levosalbutamol/levalbuterol inhalations will be recorded daily by the parent(s)/caregiver(s)/legal guardian(s) in an electronic diary/PEF meter. Each patient should be reminded that salbutamol/albuterol or levosalbutamol/levalbuterol should be used only as needed for symptoms, not on a regular basis or prophylactically. The baseline number of salbutamol/albuterol or levosalbutamol/levalbuterol inhalations/day will be based on the mean of the 7 days prior to randomization.

9.2.2.3 Health Care Resource Utilization

The HCRU questionnaire (questions on use of reliever medication, specialist visit, hospitalization, emergency or urgent medical care facility visit, outcome, school days' loss, etc), as integrated part of the e-CRF, will be administered as shown in [Section 1.2](#), and will additionally be used to assess HCRU in the event of any asthma exacerbation: severe asthma exacerbation event or evidence of LOAC (for detailed definitions see [Section 9](#)).

9.2.2.4 Patient Reported Outcomes, Including Health Related Quality of Life (Secondary Endpoints)

Patients will be administered the following PRO questionnaires by their parent(s)/caregiver(s)/legal guardian(s) or with their help. The interviewer administered versions are only for children: ACQ-IA, paediatric asthma quality of life questionnaire (PAQLQ[S]-IA) and will be administered by an interviewer (clinic staff designated by Investigator).

9.2.2.4.1 Asthma Control Questionnaire–Interviewer Administered

The ACQ-IA was designed to measure both the adequacy of asthma control and change in asthma control, which occurs either spontaneously or as a result of treatment, and will be used for children 6 years to <12 years old at Screening.

9.2.2.4.1.1 ACQ-7-IA (Asthma Control Questionnaire–Interviewer Administered, 7-question version)

The Asthma Control Questionnaire–Interviewer Administered, 7-question version (ACQ-7-IA) has 7 questions, with the first 5 items of ACQ-7 (ACQ-5-IA score) addressing the most common asthma symptoms: 1) frequency in past week awoken by asthma during the night, 2) severity of asthma symptoms in the morning, 3) limitation of daily activities due to asthma, 4) shortness of breath due to asthma and 5) wheeze. And with 2 questions on overall reliever medication use 6) short-acting bronchodilator use, and – after spirometry assessment – current asthma status: 7) predicted bronchodilator use of FEV1 (pre-bronchodilator use, % and % predicted use).

Patients and/or parent(s)/caregiver(s)/legal guardian(s) are asked to recall how their asthma and/or their child's asthma, respectively, has been during the previous week and to respond to the symptom questions 1) to 6) on a 7-point scale (0 = no impairment, 6 = maximum impairment).

After spirometry assessment, patients and/or parent(s)/caregiver(s)/legal guardian(s) are asked to recall how their asthma and/or their child's asthma has been during the previous week and to respond to the symptom and bronchodilator use questions on a 7-point scale (0=no impairment, 6= maximum impairment). Clinic staff scores the % predicted FEV1 on a 7-point scale based on the pre-central reading spirometry result displayed immediately after the testing. Then, the questions are equally weighted and the global ACQ-7 score is the mean of the 7 questions and therefore between 0 (totally controlled) and 6 (severely uncontrolled) (see [Appendix F](#)).

Higher score indicates lower asthma control. Patients with a score below 1.0 reflect adequately controlled asthma and patients with scores above 1.0 reflect inadequately controlled asthma. On the 7-point scale of the ACQ-7, a change or difference in score of 0.5 is the smallest change that can be considered clinically important, corresponding to the MCID defined by the developer.

For statistical analysis, ACQ-7 global score is calculated by the sponsor using the BMS post central reading value of the %predicted FEV1 for the question 7 of the questionnaire.

Measurement properties such as reliability and ability to detect change have been documented in the literature.

9.2.2.4.1.2 ACQ-5-IA (Asthma Control Questionnaire–Interviewer Administered, 5-question version)

The ACQ-5-IA will be deduced from the responses to the first 5 questions of ACQ-7-IA and will be used for children ≥ 6 years to < 12 years old at Screening.

Higher score indicates lower asthma control. Patients with a score below 1.0 reflect adequately controlled asthma and patients with scores above 1.0 reflect inadequately controlled asthma. On the 7-point scale of the ACQ-5, a change or difference in score of 0.5 is the smallest change that can be considered clinically important, corresponding to the MCID defined by the developer.

Measurement properties such as reliability and ability to detect change have been documented in the literature (10).

9.2.2.4.2 *Pediatric Asthma Quality of Life Questionnaire with Standardized Activities–Interviewer Administered*

The PAQLQ(S)–IA was designed as an interviewer-administered PRO to measure the functional impairments that are most troublesome to children ≥ 7 years old at Randomization Visit 2, as a result of their asthma (see [Appendix G](#)). The instrument is comprised of 23 items, each rated on a 7-point Likert scales from 1 to 7.

The PAQLQ(S)-IA has 3 domains. The domains and the number of items in each domain are as follows:

- Symptoms (10 items)
- Activity limitation (5 items)
- Emotional function (8 items)

A global score is calculated ranging from 1 to 7 and a score by domain. Higher scores indicate better quality of life.

The instrument has been used in many clinical trials, and it has been shown to be reliable, valid (patient interviews), and sensitive to change. The MCID for PAQLQ(S)-IA is 0.5 (11).

9.2.3 Safety and Tolerability Endpoints

The same safety assessments will be applied across both arms. AEs, including serious adverse events (SAEs) and AEs of special interest (AESI), will be collected at any time during study. The Investigator will ask the patient and parents how he/she has felt since the last study visit. To assure the continuing safety of patients in this study, an independent DMC will be responsible for reviewing the safety data on a periodic basis throughout the course of the study as outlined in [Section 6.4.1](#).

Safety observations

- The Investigator should take all appropriate measures to ensure the safety of the patients. Notably, he/she should follow up the outcome of SAEs/AESI until clinical recovery is complete and laboratory results have returned to normal or until progression has been stabilized or death. In all cases, this may imply that observations will continue beyond the last planned visit per protocol, and that additional investigations may be requested by the Sponsor.
- Patient height will be recorded at randomization as baseline value and compared with last height available during randomized treatment.
- When treatment is prematurely discontinued, the patient's observations will continue until the end of the study as defined by the protocol for that patient.
- In case of any SAE/AESI with immediate notification brought to the attention of the Investigator at any time after the end of the study for the patient and considered by him/her to be caused by the investigational product with a reasonable possibility, this should be reported to the Sponsor.

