Additionally, the long term adverse effects of systemic and ICS on bone metabolism, adrenal function, and growth in children lead to attempts to minimize the amount of corticosteroid usage. Lastly, the consequences of unresponsiveness to therapy or lack of compliance with therapy are evidenced by loss of asthma control (LOAC), which can be severe (ie, severe asthma exacerbation event) and possibly life-threatening. The poor response of some patients with asthma may reflect the number of cellular and molecular mechanisms operative in asthma. There is increasing interest in distinct phenotypes because targeted therapy is more likely to be successful in patients with similar underlying pathobiologic features (4). Recent therapeutic approaches in asthma have been focused on trying to control type 2 inflammation. A vast majority of 6-11 years old with asthma show evidence of type 2 inflammation characterized by upregulation of inflammatory cytokines, interleukin-4 (IL-4), interleukin-5 (IL-5), and interleukin-13 (IL-13). The most recent GINA guidelines (1) for management of severe asthma report that for patients with severe asthma, type 2 inflammation can be identified by elevated peripheral eosinophils (≥ 150 cells/ μ L) and/or elevated FeNO (≥ 20 ppb), and/or sputum eosinophils $\geq 2\%$, and/or asthma that is clinically allergen-driven. Up-regulation of IL-4 and IL-13 activity has been implicated as an important inflammatory component of asthma disease progression. Dupilumab is under development as a potential novel treatment for asthma. Dupilumab, a fully human monoclonal antibody, is directed against the IL-4 receptor alpha subunit (IL-4R α), which is a component of IL-4 heterodimeric receptors Type I (IL4-ligand only) and Type II (both IL-4 and IL-13 ligands). The binding of dupilumab to IL-4R α results in blockade of downstream signaling initiated by both IL-4 and IL-13. For complete information regarding the preclinical and clinical evaluation of dupilumab to date, see the Investigator's Brochure.

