9.2.3.2 Vital Signs

Vital signs blood pressure (mmHg), heart rate (beats per minute), respiratory rate (breaths per minute), body temperature (degrees Celsius), and will include height (cm) and body weight (kg), measured at the Screening and Randomization Visits (Visits 1 and 2) and every subsequent visit. Height will be measured with a proper stadiometer at every visit. Stadiometer measurements will be made without patient wearing shoes. Vital signs will be measured at clinic visits, in sitting position, using the same arm at each visit, and prior to administration of investigational product.

Refer to [Section 1.2](#) Study Flow Chart for the schedule of vital signs performed throughout this study.

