11.4.3.2 Clinical Laboratory Evaluation, Vital Signs and Electrocardiogram Data

Results and change from baseline for the parameters will be summarized by treatment group for baseline and each post baseline time point, endpoint, minimum and maximum value. Summary statistics will include number of patients, mean, SD, median, Q1, Q3, minimum and maximum. The descriptive by visit analysis will be conducted from the baseline up to the scheduled evaluation visit for all patients disregarding the treatment status of the patients at each visit as long as their data is available.

The proportion of patients who had at least one incidence of PCSA at any time during the treatment-emergent period will be summarized by treatment group. Shift tables showing changes with respect to the baseline status will be provided.

Listings will be provided with flags indicating clinically out-of range values, as well as PCSA values.

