2.1.4.4 Vital signs variables

Vital signs blood pressure (mmHg), heart rate (beats per minute), respiratory rate (breaths per minute), body temperature (degrees Celsius), and will include height (cm) and body weight (kg), measured at the Screening and Randomization Visits (Visits 1 and 2) and every subsequent visit. Height will be measured with a proper stadiometer at every visit. Stadiometer measurements will

be made without patient wearing shoes. Vital signs will be measured at clinic visits, in sitting position, using the same arm at each visit, and prior to administration of investigational product.

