2.4.5.4 Analyses of vital sign variables

The analyses of vital sign data will be performed in the safety population. The summary statistics (including number, mean, median, Q1, Q3, standard deviation, minimum and maximum) of all vital signs variables (values and changes from baseline) will be calculated for each visit or study assessment (baseline, each postbaseline time point, last on-treatment and/or worst on-treatment value) by treatment group. For all parameters, mean changes from baseline with the corresponding standard error will be plotted over time (at same time points) in each treatment group.

The incidence of PCSAs at any time during the treatment-emergent adverse event period will be summarized by treatment group irrespective of the baseline level and/or according to the following baseline status categories:

- Normal/missing
- Abnormal according to PCSA criterion or criteria

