	28 days/1 month to 23 months old (Infants)	≤34 mmHg and decrease from baseline ≥10 mmHg ≥54mmHg and increase from baseline ≥10 mmHg	
	24 months/2 years to <6 years old (Children)	≤34 mmHg and decrease from baseline ≥10 mmHg ≥59mmHg and increase from baseline ≥10 mmHg	

**CRITERIA for POTENTIALLY CLINICALLY SIGNIFICANT ABNORMALITIES
For Studies in Children**

Parameter	Age range	PCSA	Comments
	6 to <12 years old (Children)	≤48 mmHg and decrease from baseline ≥10 mmHg ≥72mmHg and increase from baseline ≥10 mmHg	
	12 to 16/18 years old (Adolescents)	≤54 mmHg and decrease from baseline ≥10 mmHg ≥78mmHg and increase from baseline ≥10 mmHg	
Orthostatic hypotension	All age ranges	SBP : St — Su ≤ - 20 mmHg DBP : St — Su ≤ - 10 mmHg	
Temperature	All age ranges	Rectal, ear or temporal artery: ≥100.4 °F/38.0 °C Oral or pacifier: ≥99.5 °F/37.5 °C Axillary or skin infrared: ≥99 °F/37.2 °C	Ear temperature not accurate below 6 months of age
Respiratory rate	Birth/0 to 27 days old (Neonates)	<30 per minutes >60 per minutes	Based on normal range
	28 days/1 month to 23 months old (Infants)	<24 per minutes >40 per minutes	
	24 months/2 years to <6 years old (Children)	<22 per minutes >34 per minutes	
	6 to <12 years old (Children)	<18 per minutes >30 per minutes	
	12 to 16/18 years old (Adolescents)	<12 per minutes >20 per minutes	
SaO2	All age ranges	≤95 %	
Weight	All ranges	≥5 % weight loss from baseline	Based on identification of trends in the child's growth with a series of visits WHO Multicentre Reference Study Group, 2006; Center for Disease Control. Growth chart 2007

**CRITERIA for POTENTIALLY CLINICALLY SIGNIFICANT ABNORMALITIES
For Studies in Children**

Parameter	Age range	PCSA	Comments
Clinical Chemistry			Ref Molleston JP et al. JPGN 2011; Moritz et al., Pediatrics 1999; Moritz et al., Pediatr Nephrol 2005 ; Sedlacek et al., Seminars in Dialysis 2006) Gong G et al. Clinical Biochemistry 2009; Masilamani et al. Arch Dis Children 2012; Mulberg AE et al. Pediatric Drug Development Concepts and applications. John Wiley & sons, Inc. 2009
ALT/SGPT	All age ranges	≥ 3 ULN By distribution analysis: ≥ 3 ULN ≥ 5 ULN ≥ 10 ULN ≥ 20 ULN	Based on normal ranges: 6 to 50 U/L (0-5 days), 5 to 45 U/L (1-19 years)
AST/SGOT	All age ranges	≥ 3 ULN By distribution analysis: ≥ 3 ULN ≥ 5 ULN ≥ 10 ULN ≥ 20 ULN	Based on normal ranges: 35 to 140 U/L (0-5 days), 15 to 55 U/L (1-9 years), 5 to 45 U/L (10-19 years)

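### Height is analysed only in raw centimetres, and the one height comparison the protocol names depends on how long each child stayed on treatment

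*Protocol*

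**What the plan says.** **What is named.** Among the safety observations in Protocol 9.2.3: "Patient height will be recorded at randomization as baseline value and compared with last height available during randomized treatment". The sentence gives no scale, no fixed time point and no adjustment.

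**What is measured.** Protocol 9.2.3.2: "Height will be measured with a proper stadiometer at every visit". SAP 2.1.4.4 places it with the vital signs, which "will include height (cm) and body weight (kg), measured at the Screening and Randomization Visits (Visits 1 and 2) and every subsequent visit".

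**What is analysed.** Protocol 11.4.3.2, which covers vital signs: "Results and change from baseline for the parameters will be summarized by treatment group for baseline and each post baseline time point". The same section takes all children with data into the by-visit summaries, whether or not they are still on treatment. SAP 2.4.5.4 says that summary statistics "of all vital signs variables (values and changes from baseline) will be calculated for each visit or study assessment". The last and/or worst on-treatment value is among those assessments, and mean change is also plotted by arm at matched times. Table 12 in SAP 2.5.4 sets the Week 52 vital-sign window at days 351 to 378. SAP 2.4.5 describes the safety analysis as essentially descriptive, without systematic testing.

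**What is absent.** Neither document plans a standardised height score, a height percentile, or a height analysis adjusted for age or sex. The vital-sign criteria in SAP Appendix A include a 5% "weight loss from baseline" but have no height entry.

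**Why height is of interest.** Protocol Section 4 cites "the long term adverse effects of systemic and ICS on bone metabolism, adrenal function, and growth in children" as a reason to limit corticosteroid use.

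**The concern.** These are children aged 6 to under 12. How many centimetres a child grows depends on age, sex and elapsed time. The last on-treatment height falls at a different time for each child who stops early, so a raw change to that height combines growth rate with time on treatment. This is the only comparison the protocol singles out for height.

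Raw centimetres also cannot show whether a given child is growing as expected for age and sex. The SAP accepts this principle for lung function: Table 3 in SAP 1.6 drops age, sex and height from the FEV1 model because percent predicted FEV1 already accounts for them. Height itself is given no such scale.

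At stake is how clearly the trial can describe growth under treatment, in either direction. Corticosteroid effects on growth are part of its rationale, and SAP 2.4.4.5.2 compares systemic corticosteroid exposure by arm.

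**Working it through.** **1. The plan's own figure.** Protocol 11.1 assumes 20% linear discontinuation at one year and a mean exposure of 0.9 year. With stops uniform over the year:

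- E[T] = 0.8 × 1 + 0.2 × 0.5 = 0.90 year, which matches.
- E[T²] = 0.8 + 0.2/3 = 0.8667
- Var(T) = 0.8667 − 0.81 = 0.0567, so SD(T) = 0.238 year.

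**2. Spread that time on treatment adds to change to last height.** The documents give no growth rate, so 4.5 to 6.5 cm/year is an assumption. The added SD is velocity × 0.238:

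- 4.5 × 0.238 = 1.07 cm
- 6.5 × 0.238 = 1.55 cm

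**3. The same quantity at Week 52.** The window spans 378 − 351 = 27 days. Even end to end that is worth only 4.5 × 27/365.25 = 0.33 cm to 6.5 × 27/365.25 = 0.48 cm. The by-visit summary therefore removes nearly all of the time problem.

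**4. Shift between arms.** Expected spurious difference = (difference in stopping proportion) × 0.5 year × velocity.

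- Equal stopping, as the plan assumes: 0.
- 10 points apart (assumed): 0.10 × 0.5 × 4.5 = 0.23 cm to 0.10 × 0.5 × 6.5 = 0.33 cm.
- 10% versus 30% (assumed): 0.45 to 0.65 cm.

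**5. Precision of the two planned comparisons.** No test is planned, so power serves here only as a yardstick. Inputs: 268 and 134 children, an assumed true slowing of 0.5 cm/year, and an assumed between-child velocity SD of s. Measurement error is ignored.

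- Last available: effect 0.5 × 0.9 = 0.45 cm; SD = √(0.8667 s² + 0.0567 v²), with v the growth velocity.
- Week 52: effect 0.5 cm; SD = s; 80% of each arm, taken as if every child who stops is also missing.

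| s (cm/year) | Last available, v = 4.5 to 6.5 | Week 52 by visit |
|---|---|---|
| 1.0 | 85% to 65% | 99% |
| 1.5 | 68% to 53% | 80% |
| 2.0 | 51% to 42% | 56% |

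The comparison that the protocol names is the weaker of the two in every row. The stronger one is already planned, but only as a raw mean.

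**6. What raw centimetres still lose at Week 52.** Randomisation is stratified by ICS dose, eosinophil count and region (Protocol 11.1), not by age or sex. Any chance imbalance in those two passes unadjusted into the raw Week 52 difference, and the variation they explain stays in its standard error. If they explain a fraction R² of the variance in change, removing it multiplies the standard error by √(1 − R²). The documents give no basis for R², so this gain cannot be sized here.

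**The case against.** The strongest reply is that a fair comparison is already planned. Change in height is tabulated and plotted by arm at fixed visits, and under Protocol 11.4.3.2 this covers children who have stopped treatment, who are also asked to keep attending. The sentence in Protocol 9.2.3 is one item in a list of safety observations, outside the statistical section. No objective concerns growth, and a standardised score could be derived later from data already held. All of this stands, and it sets the size of the point.

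It also rules out several stronger readings that a reader might infer:

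- *Growth is compared only at the last available height.* It is not; the by-visit analysis is planned in both documents.
- *The contrast between arms is mixed with age.* Randomisation balances age and sex in expectation. Raw centimetres cost precision and leave chance imbalance; they do not bias the comparison.
- *A spurious difference should be expected.* That needs stopping rates that differ between arms, and the plan assumes a single rate.
- *Dividing the last-available change by time would cure it.* Short follow-up inflates measurement error. With 20% stopping uniformly and a first height at Week 2 (1/26 year), error variance is multiplied by about 0.8 + 0.2 × (26 − 1) = 5.8, which can cancel the gain.
- *A child who stops growing would go unnoticed.* Appendix A would not flag that child. However, height and weight are taken at each clinic visit, physical examinations are repeated, and vital-sign abnormalities needing consultation or treatment are recorded as adverse events (Protocol 10.4.3).

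The reply does not supply an age-appropriate scale or an adjusted estimate, and it leaves the follow-up-dependent comparison as the one the protocol names.

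**Conclusion.** The point holds as a cheap improvement to a descriptive safety analysis. Height is well measured but analysed only in raw centimetres, and the comparison named in Protocol 9.2.3 depends on time on treatment. That dependence adds an SD of 1.07 to 1.55 cm, given the plan's 20% linear discontinuation and an assumed growth of 4.5 to 6.5 cm/year.

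The planned Week 52 mean avoids most of it. What remains is lost precision, unadjusted chance imbalance in age and sex, and no scale on which one child's growth can be read against age and sex. The precision loss cannot be quantified from the documents. They do not support a claim that the between-arm height comparison is biased, or that a growth effect would necessarily be hidden.

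**What to change.** In SAP 2.4.5.4:

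- Derive height and weight standard-deviation scores for sex and age, using one named growth reference. Compute age at the visit date, because SAP 2.5.1 defines age as whole years at consent.
- Report change in score from baseline to Week 52 by arm, with the dupilumab minus placebo difference and 95% CI adjusted for baseline score. Present it descriptively, without a test.
- Include every child with a Week 52 height, regardless of treatment status.

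Name this as the height comparison in place of the last-available one in Protocol 9.2.3; Table 3 of the SAP, which lists changes from the protocol's planned analyses, is a natural place to record it. The existing raw by-visit tables can stay.

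The cost is SAP wording and a few derived variables from height, weight, sex and birth date. The real downside is that a single growth reference must be chosen for a multinational sample. The change does nothing for children with no Week 52 height.
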